### **10.3.4. Missing, Unused, and Spurious Data**

All available efficacy and safety data will be included in data listings and tabulations. For the primary efficacy criterion analysis, subjects with a reduction in bone marrow fibrosis score by at least one grade according to WHO criteria (central adjudication) at any post baseline visit will be considered as responders. Subjects without any central assessment of bone marrow fibrosis will be considered as non-responders. In addition, subjects who discontinue due to toxicity prior to completion of one cycle of study drug will also be considered non-responders for the efficacy analyses.

Except for the imputation of missing values for the analysis of the primary criterion as described above, all other analyses will be based on observed data only; no missing data will be imputed.

### **10.3.5. Interim Analyses**

There is no interim analysis planned.

### **10.3.6. Software used for statistical analyses**

The < SAS software, version 9.2 or higher >, will be used for the statistical analysis.

## **10.4 Protocol deviations**

Major protocol deviations are defined as deviations liable to prevent or change the interpretation of the results of the primary efficacy analysis of the study. The following deviations will be considered as major (this list is not exhaustive and will be reviewed at the time of the blind review meeting):

- non compliance with the inclusion or non inclusion criteria
- non compliance with study treatment
- no post-baseline data for the primary efficacy endpoint
- intake of forbidden medication

All other deviations will, a priori, be considered as minor deviations. However, all deviations will be reviewed and adjudicated as either major or minor during the blind review meeting before database lock and code break.

## 10.5. Analysis datasets

The statistical analysis will be conducted on the following subject data sets:

### 10.5.1. Efficacy Analysis Sets:

**The Full Analysis Set (FAS)** will consist in all randomized subjects having received at least one administration of the study medication with at least one post-baseline assessment of BMRR (primary efficacy criterion) available. Subjects who discontinue due to toxicity prior to completion of one cycle of study drug will also be kept in the FAS and considered non-responders for the efficacy analysis.

The full analysis set will be the primary population for the efficacy analyses in this trial.

**The Per Protocol (PP) set:** a subset of the FAS consisting of all subjects who are randomized, and who did not present any major protocol deviations, who are evaluable based on having received at least 3 cycles of study drug, and who have an ORR measurement. The per-protocol set will be used for secondary analyses of the primary efficacy criterion and for the analysis of some selected secondary efficacy criteria.

### 10.5.2. Safety Analysis Sets:

**The Safety (SAF) dataset:** composed of all randomized subjects having received at least one dose of study drug and having a post-baseline safety observation. This data set will be used to perform the analysis of safety.

## 10.6. Planned Statistical Analyses and Methods

### 10.6.1 Efficacy Analyses

#### 10.6.1.1. Primary analysis of efficacy

The primary efficacy analysis will consist in computing the bone marrow response rate (percent of subjects with a reduction in bone marrow fibrosis score by at least one grade, see Section 3.1) and its 95% (unadjusted) and 97.5% (adjusted) two-sided confidence intervals within each treatment arm. This analysis will be conducted on the FAS analysis set.

Inferential interpretation: for the 3 mg/kg and 10 mg/kg arms, the lower limit of the 97.5% two-sided confidence interval will be compared to 10%, a threshold assumed to define the minimal clinically relevant effect. If the lower limit of the confidence interval is above 10%, the corresponding dose will be claimed to have demonstrated clinically relevant efficacy.

The confidence intervals computation will use a method consistent with the stratified design.

#### 10.6.1.2. Sensitivity analyses on the primary endpoint:

**Sensitivity analyses on the FAS:**

To further examine a potential stratum effect, the BMRR and its confidence interval will be computed for each dose arm within each stratum, at least for the dose by stratum combination cells with sufficiently large sample sizes (i.e. greater than 10).

#### **Sensitivity analyses on the PP set:**

The analysis described above in Section 10.6.1.1. for the primary analysis on the FAS will be repeated on the PP analysis.

### **10.6.1.3. Secondary and exploratory efficacy analyses:**

#### **10.6.1.3.1. Comparison of PRR between treatment arms**

Pairwise comparisons between the three dose groups will be performed using the Cochran-Mantel-Haenszel (general association) statistic in the SAS Freq procedure, to take into account the stratified design, using the following statement:

*tables Stratum\*Treatment\*Response / cmh;*

The Breslow-Day Test for Homogeneity of the Odds Ratios will be examined to detect a potential significant stratum difference in the odds ratios.

Two pairwise comparisons (3 mg/kg versus 0.3 mg/day and 10 mg/kg versus 0.3 mg/day) will be computed with the aim to demonstrating superiority and, consequently, will use an adjusted a two-sided 0.025 level of significance.

The third comparison (10 mg/kg versus 3 mg/kg) is not expected to have enough power to demonstrate any difference with the planned sample size. This comparison is considered exploratory and will be conducted using an unadjusted 0.05 level of significance.

These analyses will be computed on both the FAS (primary analysis set) and PP analysis sets.

#### **10.6.1.3.2. Analyses of categorical secondary and exploratory efficacy endpoints:**

Percentages and or rates will be computed, together with their 95% confidence intervals, within each treatment arm.

#### **10.6.1.3.3. Analyses of quantitative secondary and exploratory efficacy endpoints:**

Descriptive statistics for quantitative variables (see Section 10.3.2) will be computed, together with the 95% CI of the mean (or median depending on the variable)

#### **10.6.1.3.4. Inferential analyses for secondary and exploratory efficacy endpoints:**

For all categorical or quantitative secondary efficacy endpoints, formal pairwise between arms comparisons will be computed. These comparisons will use a two-sided 0.05 level of significance, hence without any correction for multiplicity (See section 10.3.3). The results of these tests will have to be interpreted cautiously bearing in mind the issue of multiplicity and the increased risk of erroneously obtaining statistically significant results.

No between arms comparisons will be computed for the exploratory efficacy endpoints, only descriptive analyses will be computed.

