#### 3.2. Secondary Endpoints

The secondary endpoints for the study are:

- Comparison of primary and secondary efficacy parameters between doses
- Incidence of adverse events (AEs), serious adverse events (SAEs), and changes in laboratory test results
- Bone marrow improvement:
  - Bone marrow response rate at weeks 12, 24, and 36
  - Duration of bone marrow response
- Hemoglobin improvement

Baseline Status	Categories of Hemoglobin Improvement
Subjects who are transfusion dependent ( $\geq 2$ units PRBC every 4 weeks for 12 weeks prior to or after C1D1), regardless of baseline hemoglobin level	Percent of subjects with Red cell transfusion independence (no transfusions for $\geq 12$ consecutive weeks)  OR  50% reduction in RBC transfusions for $\geq 12$ consecutive weeks
Subjects with baseline hemoglobin $< 100$ g/L AND Not transfusion dependent	Percent of subjects with $\geq 10$ g/L and $\geq 20$ g/L increase in hemoglobin for $\geq 12$ consecutive weeks without transfusions

- Platelet improvement

Baseline Status	Categories of Platelet Improvement
Subjects who are transfusion dependent ( $\geq 2$ platelet transfusions in any 12 weeks prior to or after C1D1), regardless of baseline platelet level	Percent of subjects with: Platelet transfusion independence (no transfusions for $\geq 12$ consecutive weeks)  OR

Platelet transfusion = either 1 unit apheresed (single donor) platelets or 4-8 units pooled random donor platelets	50% reduction in platelets transfusions for $\geq$ 12 consecutive weeks
Subjects with $25 < \text{baseline platelets} < 50 \times 10^9/\text{L}$  AND Not platelet transfusion dependent	Percent of subjects with: Doubling of baseline platelet count for $\geq$ 12 consecutive weeks without platelet transfusions  OR  Platelet count $> 50 \times 10^9/\text{L}$ for $\geq$ 12 consecutive weeks without platelet transfusions,
Subjects with baseline platelet count $< 25 \times 10^9/\text{L}$  AND Not platelet transfusion dependent	Percent of subjects with: Doubling of baseline platelet count for $\geq$ 12 consecutive weeks without platelet transfusions  OR  Platelet count $> 25 \times 10^9/\text{L}$ for $\geq$ 12 consecutive weeks without platelet transfusions

- Hematologic improvement

Baseline Status	Categories of Hematologic Improvement

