Subjects with both Hemoglobin $< 100 \text{ g/L}$ and Platelets $< 50 \times 10^9/\text{L}$	Percent of subjects who have EITHER Hemoglobin improvement OR Platelet improvement as described above and no worsening of hemoglobin or platelets from baseline
Subjects with only Hemoglobin $< 100 \text{ g/L}$	Percent of subjects who have Hemoglobin improvement as described above  AND Did not develop platelets $< 50 \times 10^9/\text{L}$
Subjects with only Platelets $< 50 \times 10^9/\text{L}$	Percent of subjects who have Platelet improvement as described above  AND Did not develop Hemoglobin $< 100 \text{ g/L}$ or new transfusion dependence

- Symptom improvement:

- Percent of subjects with 25% and 50% reduction in MPN-SAF Total Symptom Score from baseline at Week 36
- Mean change from baseline in EORTC QLQ-C30 at 36 weeks
- Duration of all improvement parameters listed above
- Percent of subjects with complete response, partial response, clinical improvement, stable disease, and progressive disease according to IWG-MRT criteria (Tefferi 2013, APPENDIX B)

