## 10. STAGE 2 PLANNED STATISTICAL METHODS

### 10.1 Determination of Sample Size

The chosen sample size of 72 subjects (i.e. 24 subjects per dose arm) is deemed sufficient to provide adequate precision to the estimation of the response rate in each treatment arm. The trial will enroll 84 subjects to allow for a discontinuation rate of 15%.

On the basis of the available data, it is assumed that the response rate on the primary endpoint will be 5% in the 0.3 mg/kg arm, 46% in the 10 mg/kg arm and at least 46% in the 3 mg/kg arm. A sample size of 24 subjects will ensure an absolute precision of +/- 8% to the evaluation of the response rate in the 0.3 mg/kg arm (assuming the response rate is 5%) and an absolute precision of +/- 20% of the response rate in the 3 mg/kg and 10 mg/kg arms (assuming the response rate is 46%).

In addition, with 24 subjects in each arm, the probability to demonstrate that the observed response rate in the 3 mg/kg and 10 mg/kg arms is larger than 10% by comparing the lower limit of the exact 97.5% two-sided confidence interval of the observed rate to 10% is larger than 0.999 (assuming the response rate is 46%)

In addition, it is planned to perform pairwise comparisons between dose arms as part of the secondary efficacy analysis. A sample size of 24 subjects per arm will ensure a power of 82% to detect a difference of 39% between two treatment arms (assuming the best response rate is 46%) with a two-sided type one error of 0.025. Consequently if the assumption of response rates of 5% in the 0.3 mg/kg arm and 46% in the 3 and 10 mg/kg arm is true, the study will be sufficiently powered (power = 82%) to demonstrate a significant superiority of any of the higher doses over the smallest dose, using an adjusted two-sided 0.025 type-one error rate.

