2.2.2 Secondary Efficacy Endpoints

The secondary efficacy endpoints are as follows for:

Stage 1:

- Bone Marrow MF grade shifts relative to baseline over time
- Modified Myeloproliferative Neoplasm-Symptom Assessment Form Total Symptom Score (MPN-SAF TSS) changes from baseline over time

Stage 2:

- Bone Marrow improvement:
 - Bone marrow (BM) response rate (MF Grade) at each visit (reduction of 1 grade versus baseline)
 - Duration of BM response defined for responding subjects as time from first decrease from baseline of one grade to time of return to baseline levels. If no return to baseline levels or worse than baseline then duration will be censored at the last BM assessment.
- Hemoglobin improvement (number and percentage of subjects):
 - For red blood cell transfusion dependent subjects at baseline (at least 2 units every 4 weeks for 12 weeks prior to Cycle [C]1Day [D]1), improvement is defined as either:
 - 1) absence of any packed red blood cells (PRBC) transfusion during any consecutive 12 weeks interval with hemoglobin level of ≥80g/L

OR

- 2) at least a 50% reduction in PRBC transfusions for 12 consecutive weeks with hemoglobin level of ≥80g/L
- For red blood cell transfusion independent subjects improvement is defined as:
 - ≥10 g/L increase in hemoglobin level for 12 consecutive weeks without transfusions
- Platelet improvement (number and percentage of subjects)

- For transfusion dependent subjects at baseline, improvement is defined as either:
- 1) becoming transfusion independent for 12 consecutive weeks

OR

- 2) reduction in transfusions need ≥50% from baseline for 12 consecutive weeks
- For transfusion independent subjects with baseline platelet count below 100^9/L, improvement is defined as:
 - ≥50% increase in the number of platelet for 12 consecutive weeks or normalization of platelet count (above lower limit normal)
- Symptom improvement:

Percent of subjects with 50% reduction in MPN-SAF TSS from baseline over time(Tefferi 2013)

• Percent of subjects with complete response, partial response, clinical improvement, stable disease and progressive disease according to IWG-MRT criteria.

2.2.3 Exploratory Efficacy Endpoints

The exploratory efficacy endpoints are as follows for:

Stage 1:

- Bone marrow biopsy results for:
 - Myeloblasts (%), at each time point and change from baseline
 - Cellularity (%), at each time point and change from baseline
 - Collagen and reticulin grade shifts relative to baseline over time

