- Myeloblasts and cellularity will be presented at baseline, Weeks 12 and 24 as well as change from baseline
- Collagen grade shifts relative to baseline at Weeks 12 and 24.

The modified MPN-SAF TSS will be presented descriptively at baseline and at the beginning of each cycle (Cycle 2 onward). In addition, the number of subjects with \geq 25% and \geq 50% reduction relative to baseline at the beginning of each cycle (Cycle 2 onward) will be presented.

Stage 2:

Duration of effect of the three doses on reduction in bone marrow fibrosis:

- To assess the duration of effect of the three doses on bone marrow improvement a
 Kaplan-Meier plot will be provided. Duration of BM improvement will be defined for
 responding subjects as time from first decrease from baseline of one grade to time of
 return to baseline levels. If no return to baseline levels then duration will be
 censored at the last BM assessment
- Effect and duration of effect of the three doses on disease related anemia, thrombocytopenia, and constitutional symptoms: For patients with improvement, the duration of improvement is defined as the number of weeks of improvement from the first12 weeks of improvement period.

IWG-MRT response will be summarized by treatment group at each visit by percent of subjects with complete response, partial response, clinical improvement, stable disease and progressive disease according to IWG-MRT criteria.

4.4.3 Exploratory Efficacy Endpoints

The exploratory endpoints will be summarized using tables, listings and graphs as appropriate.

4.4.4 Sensitivity Analyses

For Stage 2, a non-stratified analysis of BMRR will be computing as a sensitivity analysis.

4.4.5 **Subgroup Analyses**

Stage 1:

• Primary endpoint results will be presented by risks groups (intermediate-1, intermediate-2, or high risk subjects).

Stage 2:

- Primary endpoint results will be presented:
 - by risks groups (intermediate-1, intermediate-2, or high risk subjects)
 - for each strata separately (baseline anemia alone, baseline thrombocytopenia alone, baseline anemia and thrombocytopenia)
 - by transfusion status at baseline with transfusion dependency defined as: ≥ 2
 units PRBC every 4 weeks for 12 weeks prior to or after C1D1
 - by PTX-2 level at baseline classify by High/Low category (median as the cutoff)

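### The protocol's rule to test every secondary efficacy endpoint between doses takes in durations that exist only in responders, and the SAP does not withdraw it

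*Protocol*

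**What the plan says.** Protocol 10.6.1.3.4 sets the rule for secondary endpoints: "For all categorical or quantitative secondary efficacy endpoints, formal pairwise between arms comparisons will be computed". It continues: "These comparisons will use a two-sided 0.05 level of significance, hence without any correction for multiplicity". No endpoint is excepted. Sections 10.3.3 and 10.6.1.3.4 attach one caution to these tests, which is multiplicity.

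Protocol 3.2 lists among the secondary endpoints "Duration of bone marrow response" and, after the hemoglobin, platelet, hematologic and symptom items, "Duration of all improvement parameters listed above". The same list makes the dose contrast an endpoint in itself: "Comparison of primary and secondary efficacy parameters between doses". SAP Appendix 3 repeats that item.

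The SAP restricts duration to subjects who have something to measure. Section 2.2.2 reads: "Duration of BM response defined for responding subjects as time from first decrease from baseline of one grade". Section 4.4.2 repeats this and defines duration of the anemia, thrombocytopenia and symptom improvements for patients with improvement. For marrow-response duration, 4.4.2 says that a "Kaplan-Meier plot will be provided", as the means of assessing how long the effect of the three doses lasts. It names no between-arm test of any duration.

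**The concern.** Randomisation makes the three arms comparable as wholes. It does not make the responders in one arm comparable with the responders in another, because dose itself affects who becomes a responder. A between-arm test of duration among responders therefore mixes any effect on persistence with a difference in the kind of subject who responds. The bias can go either way, and a multiplicity warning does not address it.

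Stage 2 has no control arm, and Protocol 1.5 says that a dose response in the secondary comparisons will count as evidence of efficacy. Duration of effect on marrow fibrosis is a named secondary objective (Protocol 2.2). A reader of the study report could take a responder-only p-value as dose-response evidence that randomisation does not support.

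**Working it through.** **Inputs.** Protocol 10.1 gives 24 subjects per arm (72 in total), 84 enrolled (84/3 = 28 per arm), and response rates of 46% at 10 mg/kg and at least 46% at 3 mg/kg. For the lowest dose, "it is assumed that the response rate on the primary endpoint will be 5% in the 0.3 mg/kg arm". Biopsies after baseline are at Weeks 12, 24 and 36 (Protocol 7.11.1).

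**The plan's own figure.** Protocol 10.1 states 82% power for a 39-point difference with a best rate of 46%, so 7% versus 46%, at two-sided 0.025. With a pooled-variance normal approximation:

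- mean rate = (0.07 + 0.46)/2 = 0.265
- null standard error = √(2 × 0.265 × 0.735/24) = 0.1274
- alternative standard error = √((0.07 × 0.93 + 0.46 × 0.54)/24) = 0.1143
- power = Φ((0.39 − 2.241 × 0.1274)/0.1143) = Φ(0.914) = 0.82

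The stated figure is reproduced, so 24 per arm and these rates are the right basis for what follows.

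**Marrow responders available for a duration comparison** (binomial, expected = n × p):

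| Arm and assumed rate | n | Expected | P(0) | P(0 or 1) |
|---|---|---|---|---|
| 0.3 mg/kg, 5% | 24 | 1.2 | 0.29 | 0.66 |
| 0.3 mg/kg, 5% | 28 | 1.4 | 0.24 | 0.59 |
| 0.3 mg/kg, 7% | 24 | 1.7 | 0.18 | 0.49 |
| 0.3 mg/kg, 7% | 28 | 2.0 | 0.13 | 0.41 |
| 3 or 10 mg/kg, 46% | 24 | 11.0 | <0.001 | <0.001 |
| 3 or 10 mg/kg, 46% | 28 | 12.9 | <0.001 | <0.001 |

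For the first row, P(0) = 0.95^24 = 0.292 and P(0 or 1) = 0.292 + 24 × 0.05 × 0.95^23 = 0.661.

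**What a test could show.** The smallest two-sided exact rank p-value with m and k responders is 2/C(m + k, m). For 1 versus 11 it is 2/12 = 0.167. For 2 versus 11 it is 2/78 = 0.026. Summing over the binomial distributions at 5% and 46%, an exact rank test could reach 0.05 at all with probability 0.32 (n = 24) or 0.41 (n = 28). The documents name no test for duration, so the rank test is only a yardstick.

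**How selected the groups are.** At the assumed rates, the share of subjects who would respond on both 0.3 and 10 mg/kg cannot exceed 5%. So at most 5/46 = 11% of the 10 mg/kg responders are subjects who would also have responded on 0.3 mg/kg. For 3 versus 10 mg/kg the counts are adequate, but equal rates do not show that the same kind of subject responds to each dose. Comparability there is an assumption, not a result of randomisation.

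**Other durations.** The documents give no expected rates for hemoglobin, platelet, hematologic or symptom improvement, so their counts cannot be computed. The selection problem applies to them all the same.

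**The case against.** The strongest reply is that the final SAP plans no duration test. Its Stage 2 pairwise comparisons are for the primary response rate only (4.4.1), duration of marrow response gets a plot, and 2.6 calls the study non-inferential. Protocol 10.3.1 leaves detail to the SAP. It can also be said that the protocol's categorical-or-quantitative wording need not cover censored durations, that no decision rule hangs on these tests, and that the separate Stage 2 SAP of March 2018, mentioned in SAP section 1, is not among the documents and may have settled the matter.

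Much of this stands and lowers the practical consequence. It does not remove the conflict. The SAP does not withdraw the protocol rule, and its Appendix 3 keeps the between-dose comparison of secondary parameters. It also retains Stage 2 superiority tests at 0.025, so the non-inferential label cannot be taken as cancelling Stage 2 inference. The protocol has no separate time-to-event section, so the plain reading of its rule includes durations.

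Three stronger readings are tempting and are not supported:

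- **That the final analysis will run invalid duration tests.** The SAP names none.
- **That durability has no dose comparison keeping non-responders.** The marrow response rates by visit and the hemoglobin and platelet rates, most of which require 12 consecutive weeks, already count non-responders. What is missing is a statement that these carry the comparison.
- **That a better dose will look worse on duration.** This is possible in principle, but the documents give no durations, so any worked reversal would rest on invented ones.

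**Conclusion.** The concern holds as a conflict between the protocol rule and the SAP, with a bias attached if the rule is followed. As written, 10.6.1.3.4 requires between-dose tests of endpoints defined only in responders or improvers, and these are not randomised comparisons for any of the three pairs. For marrow-response duration, the two comparisons with 0.3 mg/kg would also rest on about 1.2 expected responders of 24, with a 66% chance of at most one.

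The sparsity figure depends on the plan's 5% assumption. It should not be extended to the other improvements, for which no rates are given, or to 3 versus 10 mg/kg. The selection argument depends on no rate. The conclusion also treats duration as a quantitative endpoint under 10.6.1.3.4. The primary analysis is unaffected.

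**What to change.** 1. In Protocol 10.6.1.3.4 and the SAP, state that durations defined only in responders or improvers are excluded from the formal between-arm tests. SAP section 1 places the current SAP after the Stage 2 primary analysis. If the protocol is no longer amended, put the statement in the SAP and document it in the study report, as Protocol 10.3.1 requires for changes of method.
2. Report these durations descriptively by arm, always with the number of responders. Label the SAP 4.4.2 Kaplan-Meier plot as descriptive in responders.
3. Base the dose comparison of marrow durability on the SAP's all-treated population. Use the planned proportions in response at Weeks 12, 24 and 36 with missing counted as non-response (SAP 4.9), and derive from them, for example, the proportion in response at two consecutive biopsies. A first response at Week 36 cannot meet that definition, which should be stated.
4. For the blood counts, use the planned 12-consecutive-week hemoglobin and platelet improvement rates within baseline categories fixed before the first dose. SAP 2.2.2 does this for red-cell transfusion dependence, whereas the Protocol 3.2 category also admits transfusions after the first dose.
5. A weeks-in-response variable with non-responders set to 0 is optional. It needs a stated rule for a first response at Week 36, which would otherwise score 0 like a non-response, and for dropout.

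The cost is a few sentences and one derived marrow variable, with no new data. The responder-only p-values are given up.
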